3.1.2.1.2. Maximum Severity of Local Reactions Within 7 Days After Vaccination

Redness and swelling will be measured by the participant and recorded in measuring device units (range: 1 to 21 and >21; an entry in the e-diary of 21 will denote ≥ 21) and then categorized during analysis as mild, moderate, or severe based on the grading scale in Table 5. Measuring device units can be converted to centimeters according to the following scale: 1 measuring device unit = 0.5 cm. Pain at the injection site will be assessed by the participant as absent, mild, moderate, or severe according to the grading scale in Table 5.

Table 5. Grading Scale for Local Reactions

	Mild Grade 1	Moderate Grade 2	Severe Grade 3	Grade 4 ^a
Redness	>2.0 cm to 5.0 cm (5 to 10 measuring device units)	>5.0 cm to 10.0 cm (11 to 20 measuring device units)	>10 cm (>20 measuring device units)	Necrosis or exfoliative dermatitis
Swelling	>2.0 cm to 5.0 cm (5 to 10 measuring device units)	>5.0 cm to 10.0 cm (11 to 20 measuring device units)	>10 cm (>20 measuring device units)	Necrosis
Pain (at the injection site)	Does not interfere with activity	Interferes with activity	Prevents daily activity	Emergency room visit or hospitalization for severe pain at the injection site

- a. Only an investigator or qualified designee is able to classify a participant's local reaction as Grade 4, after clinical evaluation of the participant or documentation from another medically qualified source (eg, emergency room or hospital record) or, in the case of pain at the injection site only, contact with the participant. Grade 4 local reactions will be collected on the AE case report form and assessed by the investigator using the AE intensity grading scale detailed in Section 10.2.3 of the protocol.

The following variables are derived for each participant included in the reactogenicity subset:

1. Maximum severity of each local reaction on any day (Day 1 through Day 7)

The maximum severity (highest grading) of each local reaction within 7 days after vaccination will be derived. The maximum severity will be derived as follows:

- = Missing, if values are missing for all days (Days 1-7);
- = 0, if the participant reports all reactions as "no" or a combination of missing and "no" for all days (Days 1-7);
- = *Highest grade* (maximum severity) within 7 days after vaccination if the answer is not "no" for at least 1 day.

2. Maximum severity of any local reaction on any day (Day 1 through Day 7)

The maximum severity for any local reaction will be derived as follows:

- = Missing, if values are missing for all days (Days 1-7) across all 3 local reactions;
- = 0, if the participant reports all reactions as “no” or a combination of missing and “no” for all days (Days 1-7) for all individual local reactions;
- = *Highest grade* (maximum severity) within 7 days after vaccination if the answer is not “no” for at least 1 day for at least 1 local reaction.

3.1.2.1.3. Duration of Each Local Reaction

The duration of each local reaction will be calculated in days as (resolution date of reaction - start date of reaction + 1). Resolution of the event is the last day on which the event is recorded in the e-diary or the date the event ends if it is unresolved during the participant diary-recording period (end date collected on the CRF) unless chronicity is established.

If there is no known end date, the duration will be considered unknown and set to “missing.” Participants with no reported reaction will not have a duration calculated.

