1.3. Schedule of Activities

The SoA table provides an overview of the protocol visits and procedures. Refer to Study Assessments and Procedures in [Section 8](#) for detailed information on each procedure and assessment required for compliance with the protocol.

The investigator may schedule visits (unplanned visits) in addition to those listed in the SoA table, in order to conduct evaluations or assessments required to protect the well-being of the participant.

Visit Identifier	Visit 1	Visit 2
Visit Description	Vaccination	1-Month Follow-Up
Visit Window	Day 1	28 to 35 Days After Visit 1
Type of Visit	Clinic	Clinic
Obtain informed consent	X	
Obtain participant number via IRT	X	
Obtain demography and medical history data	X	
Perform clinical assessment (and physical examination and vital signs if deemed necessary)	X	
Obtain prevaccination temperature (body)	X	
Confirm negative urine (or serum) pregnancy test (for WOCBP)	X	
Discuss contraceptive use (as appropriate)	X	
Record nonstudy vaccinations	X	X
Review concomitant medication use	X	X
Review inclusion and exclusion criteria and confirm eligibility	X	
Review temporary delay criteria	X	
Obtain blood sample for antibody assessment	~20 mL ^a	~80 mL
Obtain randomization number and product kit assignment from IRT	X	
Assist with app download or issue e-diary, issue measuring device and digital thermometer; provide e-diary training	X	
Study intervention administration	X	
Postvaccination observation (30 minutes) and acute immediate reaction assessment	X	
Provide study participant with emergency contact card	X	
Review e-diary data (daily review during the 7 days following vaccination)	X	
Review e-diary for ongoing reactogenicity, obtain stop dates, collect e-diary		X
Record adverse events and serious adverse events and obtain any missing stop dates	X	X

Abbreviations: IRT = interactive response technology; WOCBP = women of childbearing potential.

a. Blood sample must be collected before vaccination.

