8.2.4. Electronic Diary

Participants will be required to use an e-diary, installed on a provisioned device or as an application on a personal device, and will be asked to monitor and record local reactions, systemic events, and oral temperature each evening for 7 days following vaccination (Day 1 through Day 7, where Day 1 is the day of vaccination).

The e-diary allows recording of these assessments only within a fixed time window each day, thus providing the accurate representation of the participant's experience at that time.

Data on local reactions, systemic events, and oral temperature recorded in the e-diary will be transferred electronically to the e-diary vendor, where they will be available for review by investigators, their qualified designees, and sponsor staff at all times via a secure, restricted internet-based portal. At intervals agreed to by the vendor and Pfizer, these data will be transferred electronically to Pfizer for analysis and reporting. These data do not need to be recorded by the investigator in the CRF, except for the following conditions:

- If a participant withdraws because of prompted events recorded in the e-diary, the event(s) should be recorded on the AE page of the CRF, regardless of whether the investigator considers the event(s) to be clinically significant.
- The investigator or designee must obtain stop dates for any reactions ongoing on the last day that the e-diary was completed. The stop dates should be documented in the source documents and the information entered in the CRF. In the event the reaction is ongoing at the end of the study, the reaction will be marked as ongoing.

Investigators (or appropriately qualified designees) are required to review the e-diary data online at frequent intervals to evaluate participant compliance and safety. These prospectively collected occurrences of local reactions and systemic events are graded as described in Table 1, [Table 2](#), and [Table 3](#).

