- The investigator or appropriately qualified designee reviews the daily e-diary data online following vaccination to evaluate participant compliance and as part of the ongoing safety review.

8.9.2. Visit 2 – 1-Month Follow-Up (Clinic, 28 to 35 Days After Visit 1)

- Record details of any nonstudy vaccinations and concomitant medications as described in [Section 6.8](#).
- Collect a blood sample of approximately 80 mL for antibody assessment.
- Review the participant's e-diary data. Collect stop dates of any e-diary events ongoing on the last day that the e-diary was completed and record stop dates in the CRF. Collect any sponsor-provisioned e-diary.
- Record AEs and SAEs as described in [Section 8.3](#). Obtain and record any missing AE stop dates.
- Complete the source documents.
- The investigator or an authorized designee completes the CRF.

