6.1.2.1.2. Supplementary Analysis

The main analysis will also be performed for each RSVpreF lot.

To support the assessment of reactogenicity, the endpoints below, as specified in [Section 3.1.2.1](#), will be summarized as supplementary analysis with the same analysis population:

- Duration (days) of each local reaction and each systemic event after vaccination.
- Onset day of each local reaction and each systemic event after vaccination.

These continuous endpoints will be summarized by displaying n, mean, median, standard deviation, minimum, and maximum for each vaccine group and the pooled RSVpreF lots (Groups 1, 2, and 3).

[figure not shown]
The proportions of participants reporting each and any local reaction and each and any systemic event on each of the 7 days after vaccination will also be summarized.

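### Reactions with no known end date leave the duration summary, so any still ongoing at Visit 2 make the mean, and usually the maximum, too low

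*SAP*

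**What the plan says.** SAP 3.1.2.1.3 derives the duration of a local reaction as the resolution date minus the start date plus one day. For a reaction that resolves within the diary period, resolution is the last day it was recorded. Otherwise it is "the date the event ends if it is unresolved during the participant diary-recording period (end date collected on the CRF) unless chronicity is established". The rule for the remainder is: "If there is no known end date, the duration will be considered unknown and set to" missing. SAP 3.1.2.2 handles the duration of systemic events in the same way.

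Protocol 8.2.4 requires sites to seek the missing dates. The investigator or designee "must obtain stop dates for any reactions ongoing on the last day that the e-diary was completed", and the Visit 2 procedures (Protocol 8.9.2) repeat this: "Collect stop dates of any e-diary events ongoing on the last day that the e-diary was completed and record stop dates in the CRF". For reactions that have still not resolved, Protocol 8.2.4 adds: "In the event the reaction is ongoing at the end of the study, the reaction will be marked as ongoing".

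SAP 6.1.2.1.2 then lists "Duration (days) of each local reaction and each systemic event after vaccination" as a supplementary summary, giving the count, mean, median, SD and range for each vaccine group and for the pooled lots. The SAP provides no censoring rule, no lower bound and no count of ongoing reactions beside these figures. It also does not define chronicity or say what duration a chronic reaction receives.

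**The concern.** A reaction marked as ongoing at study end has no end date, so its duration becomes missing. Whether the value is missing therefore depends on the value itself: a reaction that resolves during the diary always has an end date, and one that lasts through Visit 2 never does. This is right-censoring, and the plan handles it by deletion.

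The duration summary is there to support the reactogenicity assessment, which is part of the primary safety objective, and prolonged reactions are what such a table should bring out. Under this rule a reaction that outlasts the study cannot appear in it, and nothing printed beside the table says that one occurred.

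**Working it through.** The documents give no duration figure and no count of reactions without an end date, so there is nothing of the plan's own to reproduce. Two questions can be worked through: how long a dropped reaction must have lasted, and how much dropping it changes each statistic.

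**Step 1. Minimum length of a reaction ongoing at Visit 2.** Inputs: diary onset on Day 1 to Day 7 with vaccination on Day 1 (SAP 3.1.2.1); Visit 2 at "28 to 35 Days After Visit 1" (Protocol 1.3), which is study Day 29 to Day 36; duration = end − start + 1 (SAP 3.1.2.1.3).

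| Onset | Visit 2 | Minimum duration |
|---|---|---|
| Day 7 | Day 29 | 29 − 7 + 1 = 23 |
| Day 1 | Day 29 | 29 − 1 + 1 = 29 |
| Day 7 | Day 36 | 36 − 7 + 1 = 30 |
| Day 1 | Day 36 | 36 − 1 + 1 = 36 |

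The floor is 23 days, and it rises to 36 days for the earliest onset and latest visit.

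**Step 2. Effect on the mean.** Let f be the share of reactions ongoing at Visit 2, L the lower bound on their duration, and m the mean of the rest. The plan reports m. The full mean is at least (1 − f)m + fL, so the shortfall is at least f × (L − m). With m = 2 days (assumed):

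| f (assumed) | L = 23 | L = 36 |
|---|---|---|
| 0.5% | 0.105 days | 0.17 days |
| 1% | 0.21 days | 0.34 days |
| 2% | 0.42 days | 0.68 days |
| 5% | 1.05 days | 1.70 days |

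At f = 0 the shortfall is zero.

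**Step 3. Effect on the maximum and median.** This is an illustration by simulation, with inputs that are not in the documents. There are 225 reactions (30% of the 750 planned vaccine recipients) with geometric durations. The ongoing ones are each counted at a whole number of days between 23 and 36. There were 2,000 runs per setting.

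| Mean of the rest | Ongoing | Mean, dropped → counted | Average maximum, dropped → counted | Runs in which the median changes |
|---|---|---|---|---|
| 2 days | 2 of 225 (about 1%) | 2.00 → 2.24 | 9.1 → 31.7 | 5.5% |
| 2 days | 11 of 225 (about 5%) | 2.00 → 3.34 | 9.1 → 35.3 | 31.6% |
| 3 days | 2 of 225 (about 1%) | 3.00 → 3.24 | 15.3 → 31.8 | 1.3% |
| 3 days | 11 of 225 (about 5%) | 3.00 → 4.29 | 15.1 → 35.3 | 14.9% |

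The maximum is the most exposed, since a single dropped reaction is enough to move it. The median rank shifts by only about f/2 and durations are whole days, so at about 1% the median seldom moves. A geometric distribution with mean 2 puts half the durations at exactly one day. That places the median on a boundary and makes it more sensitive than it would otherwise be.

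**Step 4. Stop dates never obtained.** These reactions were unresolved at the last diary entry, but their known minimum is only the last diary day − start + 1, which is 1 to 7 days. They may or may not have been long, so no guaranteed shortfall can be attached to them.

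**The case against.** The strongest reply is that the plan already does most of what is needed. Sites must obtain stop dates, Visit 2 collects them, Protocol 8.2.4.3 has fever measured daily until it resolves, and the SAP uses the CRF end date. What remains is a reaction still present about four weeks after a single injection, plus some unobtainable dates. SAP 5.3.1.1 describes missing reactogenicity data as minimal. The summary is supplementary, and a prolonged reaction still counts in incidence and maximum severity. A reader could also compare the count in the duration table with the number reporting the reaction and see how many durations are missing.

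Much of this stands, and it rules out several stronger readings that a reader might infer:

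- That every reaction outlasting the 7-day diary is dropped. It is not, if a stop date is obtained.
- That only the longest reactions are dropped. A reaction in a participant lost to follow-up need not have been long.
- That the maximum can never show 28 days or more. A reaction from Day 1 to Day 30 in a participant seen on Day 36 has an end date and is reported as 30 days.
- That the median is biased downward. With few affected reactions it usually does not change.
- That the summaries are biased as a matter of fact, or more so after vaccine than after placebo. The documents give no frequency in either arm.

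The reply does not remove the point. The reasoning in SAP 5.3.1.1 concerns diary days that were not transmitted, not end dates that are unknown. The gap between the two counts shows that durations are missing, but not whether they belong to ongoing reactions or to stop dates that were not found.

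**Conclusion.** The point holds as a narrow, conditional one. If any reaction is ongoing at Visit 2, the rule removes a duration of at least 23 days. The mean is then understated by at least f × (L − m), provided the rest average less than L. The maximum is understated whenever the dropped reaction outlasts every known one. The figure of 0.21 to 0.34 days at 1% rests on an assumed mean of 2 days and an assumed frequency; if no such reaction occurs, nothing changes. The lot-consistency decision, the reaction incidences and the maximum-severity tables are unaffected. The priority is modest, but the correction is cheap and the present rule hides the very reactions a duration table is meant to show.

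**What to change.** Amend SAP 3.1.2.1.3, and through 3.1.2.2 the systemic events, as follows:

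- For a reaction with no known end date, derive a minimum duration as the date last known ongoing minus the start date plus 1, and flag it as censored. State that the same applies to reactions treated as chronic.
- In SAP 6.1.2.1.2, report by group, beside each duration summary, the number of reactions ongoing at study end and the number whose end date is otherwise unknown.
- Show the maximum with a ≥ sign when it comes from a censored value.
- A Kaplan-Meier median may be added, but it is optional: with few censored values it would normally agree with the simple median.

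The cost is SAP wording and minor programming. Start dates are already derived, and the Visit 2 review of ongoing reactogenicity (Protocol 1.3) supplies the last-known date for those who attend. The downside is that some reported values become lower bounds. For participants lost before Visit 2 the last known ongoing date may be only the last diary day, so their bound will be short and carry little information.

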3.1.2.1.4. Onset Day of Each Local Reaction

The onset day of each local reaction will be derived. Onset day is defined as the first day of reporting any severity.

For the onset day of each local reaction, if the participant reports changes in severity of the local reaction, only the first day of reporting for that specific local reaction will be counted.

3.1.2.1.5. Presence of Local Reactions on Each Day

Presence (yes or no) of each and any local reaction on each of the 7 days (Day 1 through Day 7) follows the derivation as described in [Table 6](#).

Table 6. Derived Variables for Each and Any Local Reaction on Each Day

Variable	Yes (1)	No (0)	Missing (.)
Each local reaction on a specific day	The reaction is reported as “yes” with a diameter >2.0 cm for redness/swelling or “yes” for pain on a specific day.	The reaction is reported as “no” (or “yes” with a diameter ≤ 2.0 cm for redness/swelling) on that specific day.	The participant reports the specific local reaction as missing on that specific day.
Any local reaction on a specific day	Any reaction is reported as redness or swelling >2.0 cm or “yes” for pain at the injection site on a specific day.	All 3 local reactions are reported as redness or swelling ≤ 2.0 cm and pain at the injection site as “no” on that specific day.	The participant reports all 3 local reactions as missing on that specific day.

3.1.2.2. Systemic Events Within 7 Days After Vaccination

Systemic events, including fever, fatigue, headache, vomiting, nausea, diarrhea, muscle pain, and joint pain, are reported via the e-diary from Day 1 through Day 7 after vaccination, where Day 1 is the day of vaccination. The derivations for the systemic events below will be handled similarly to the way local reactions are handled for any presence of systemic events, severity level, duration, onset day, and systemic events on each and any day.

1. Presence (yes or no) of each systemic event on any day (Day 1 through Day 7) after vaccination.
2. Presence (yes or no) of any systemic event on any day (Day 1 through Day 7) after vaccination.
3. Maximum severity of each systemic event on any day (Day 1 through Day 7) after vaccination.
4. Maximum severity of any systemic event on any day (Day 1 through Day 7) after vaccination.
5. Duration of each systemic event after vaccination.
6. Onset day of each systemic event after vaccination.
7. Presence (yes or no) of each systemic event on each of the 7 days after vaccination.
8. Presence (yes or no) of any systemic event on each of the 7 days after vaccination.

The grading scale for systemic events is provided in [Table 7](#).

PFIZER GENERAL BUSINESS

[figure not shown]

Table 7. Grading Scale for Systemic Events

	Mild Grade 1	Moderate Grade 2	Severe Grade 3	Grade 4^a
Fatigue (= tiredness in diaries)	Does not interfere with activity	Some interference with activity	Prevents daily routine activity	Emergency room visit or hospitalization for severe fatigue
Headache	Does not interfere with activity	Some interference with activity	Prevents daily routine activity	Emergency room visit or hospitalization for severe headache
Vomiting	1 to 2 times in 24 hours	>2 times in 24 hours	Requires intravenous hydration	Emergency room visit or hospitalization for severe vomiting
Nausea	Does not interfere with activity	Some interference with activity	Prevents daily routine activity	Emergency room visit or hospitalization for severe nausea
Diarrhea	2 to 3 loose stools in 24 hours	4 to 5 loose stools in 24 hours	6 or more loose stools in 24 hours	Emergency room visit or hospitalization for severe diarrhea
Muscle pain	Does not interfere with activity	Some interference with activity	Prevents daily routine activity	Emergency room visit or hospitalization for severe muscle pain
Joint pain	Does not interfere with activity	Some interference with activity	Prevents daily routine activity	Emergency room visit or hospitalization for severe joint pain

- a. Only an investigator or qualified designee is able to classify a participant's systemic event as Grade 4, after clinical evaluation of the participant or documentation from another medically qualified source (eg, emergency room or hospital record) or contact with the participant. Grade 4 systemic events will be collected on the AE case report form and assessed by the investigator using the AE intensity grading scale as detailed in Section 10.2.3 of the protocol.

Fever is defined as an oral temperature of $\geq 38.0^{\circ}\text{C}$ ($\geq 100.4^{\circ}\text{F}$). The highest temperature for each day will be recorded in the e-diary. For reporting purposes, fever will be analyzed using the temperature ranges in [Table 8](#).

Table 8. Ranges for Fever

	Mild Grade 1	Moderate Grade 2	Severe Grade 3	Grade 4^a
Fever	≥38.0°C to 38.4°C (100.4-101.1°F)	>38.4°C to 38.9°C (101.2-102.0°F)	>38.9°C to 40.0°C (102.1-104.0°F)	>40.0°C (>104.0°F)

- a. Only an investigator or qualified designee is able to classify a participant's fever as Grade 4, after clinical evaluation of the participant, documentation from another medically qualified source (eg, emergency room or hospital record), or contact with the participant. Grade 4 fevers will be collected on the AE case report form and assessed by the investigator using the AE intensity grading scale as detailed in Section 10.2.3 of the protocol.

3.1.2.3. Adverse Events

AEs follow standard definitions as outlined in Appendix 2 of the protocol. Standard algorithms for handling missing AE dates and missing AE severity will be applied as described in the Pfizer Vaccine data standard rules.

The following derivations will be included for each participant, where applicable:

1. Any AE reported.
2. Any related AE reported.
3. Any immediate AE (AE start time is within 30 minutes after vaccination).
4. Any severe AE.
5. Any life-threatening AE.
6. Any AE leading to study withdrawal.

Each of the above will be derived for the below intervals:

[figure not shown]
- From the time of consent through study completion.
- From the time of vaccination through study completion.

